4.4.1.3 Technical Factors

Either 3DCRT or IMRT may be used for treatment. For 3DCRT treating the whole pelvis (WPRT), a minimum of 4-fields should be used and a 4 field plan is recommended. For IMRT, no specific field arrangement is required. RT will be delivered with megavoltage equipment at energies \geq 6 MV. Typically, except for VMAT techniques, 5 to 9 gantry angles are employed for the IMRT treatments. When using IMRT, preference will be given to using photon energies <=10MV, but higher energies will be permitted if necessary for production of a more optimal plan due to anatomic constraints.

4.4.1.4 EBRT Localization, Simulation, and Immobilization

Simulation will be CT-based in all cases. A urethrogram or MRI is recommended, but not required, to be used for target delineation. Rectal contrast is discouraged because it may distend the rectum and artificially displace the prostate in the anterior direction. Intravenous contrast is permitted but not required to assist in identifying the pelvic vessels. Patients will be positioned supine or prone on a flat tabletop with a customized thermoplastic immobilization cast or a molded foam cradle or similar immobilization for stabilization and setup reproducibility. The degree of bladder fullness should be made to duplicate the degree of fullness anticipated for daily treatment, i.e., if the patient is instructed to maintain a full bladder for treatment, he should be simulated as such (especially for cases in which image guidance is not implemented). The rectum should be kept as empty as possible; recommendation is for an enema 1-2 hours prior to simulation. CT images should be acquired at a slice thickness of ≤3 mm from L3/L4 vertebral

body to the perineum inferiorly. If Calypso beacons are used, slice thickness of 1.5-2 mm will be recommended. Target volumes and normal critical structures (as defined in section 4.4.1.5.3) will be defined in the slices in which they are visualized. The 3DCRT cases must utilize "beam's eye view" representations to define final beam aperture.

4.4.1.5 Treatment Planning/Target Volumes

4.4.1.5.1 Patients must have a composite treatment plan generated at the beginning of Plan 1 so that the final EBRT dose to critical structures is evaluated before any dose delivery has begun. Dose for initial treatment (CTV1/PTV1) will be 45.0 Gy at 1.8 Gy per fraction. If patient has N1 disease, CTV-N/PTV-N will be defined, and will received 55 Gy at 2.2 Gy per fraction during plan 1of the treatment course using simultaneous integrated boost technique (SIB). All patients with N1 disease will be treated with IMRT, and 3DCRT will not be permitted. Once this portion is completed, a cone down boost to the prostate and (proximal) seminal vesicles will be delivered by either IMRT or 3DCRT. Brachytherapy boost is not permitted on this study. For the boost, the dose to the CTV2/PTV2 will be 34.2 Gy at 1.8 Gy per fraction, for a total prostate dose of 79.2 Gy. For pelvic 3D-CRT, a 4-field technique, using opposed anterior-posterior and opposed lateral fields, is recommended. All fields should conform to the beam's-eye-view of the target. No specific field arrangement is required for IMRT, although typically 5-9 fields are used for fixed gantry treatment. Tomotherapy and VMAT/rapid arc/ smart arc IMRT technologies) also are allowed for IMRT treatment on this protocol.

4.4.1.5.2. The definition of GTV, CTV and PTV will be in accordance with the ICRU Report #50: Prescribing, Recording, and Reporting Photon Beam Therapy.

4.4.1.5.2.1 Plan 1 Pelvis, including prostate and seminal vesicles Gross Target Volume (GTV1 and GTV-N)

The GTV1 is defined by the physician as all known disease as defined by the planning CT, urethrogram, MRI, and clinical information. If a urethrogram is used, the GTV will encompass a volume inferiorly 5 mm superior to the tip of the dye and no less than the entire prostate. Prostate dimensions should be defined as visualized on CT scan. If MRI is performed, fusion of planning CT with the MRI will be performed on the treatment planning system, and MRI will be utilized to help further refine and delineate the GTV.

GTV-N will be defined as all positive pelvic nodal disease > 1.5 cm in short axis diameter seen on CT scan or MRI before initiation of hormone therapy. Nodal disease will be contoured based on the pre-hormone therapy imaging studies. If necessary, a CT simulation can be performed prior to initiation of hormone therapy as a baseline study that can be used for treatment planning purposes. At the discretion of the treating physician, nodal disease >=1cm will also be considered for GTV-N, particularly if there are multiple gross nodal disease present.

Clinical Target Volume (CTV1)

The CTV1 will include the prostate and entire seminal vesicles (SV), the obturator, external iliac, proximal internal iliac and distal common iliac nodes, using the vascular structures, up to a level corresponding to the top of L5-S1. At the treatment team's discretion, coverage can be increased to include common iliac nodes up to L4/L5 level. One can refer to the pelvic nodal atlas at the RTOG Web site (Pelvic Lymph Node Volumes for Prostate Cancer Atlas;

http://www.rtog.org/CoreLab/ContouringAtlases/ProstatePelvicLymphNodes.aspx).

The presacral nodes from L5-S1 to S3 may be included if desired depending on whether the dose constraints to the rectum are achievable (see Table 4.4.3). The CTV1 will include a 7 mm margin in 3-dimensions to the contoured iliac vessels, but not extend outside of the true pelvis, into the pelvic musculature nor into adjacent identifiable organs, such as the bladder, rectum or other bowel. Extension of the CTV into adjacent bone may be carved out. Anatomical boundaries to consider if 3DCRT is used include superiorly from L5-S1 to 0.5 cm below the tip of the urethral contrast dye inferiorly to ensure that the entire prostate gland is included (MRI can also be used to help define the apex). Lateral borders will be at least 1 cm from the pelvic brim. In the lateral fields, the external and internal iliac lymph nodes below the SI joints, and the posterior extension of the seminal vesicles should be covered. The usual posterior border is approximately S2-3, but

CT anatomy should take precedence. The inferior extent of the external iliac lymph nodes is at the top of the femoral heads. The inferior extent of the obturator lymph nodes is at the top of the symphysis publis.

If there are grossly involved nodes seen in the pelvis, this can be treated to a higher dose using a simultaneous integrated boost technique (see section 4.4.1.1 and Table 4.4.1.2). For these patients, a GTV-N will be defined as the grossly evident node based on imaging studies (> 1.5 cm for solitary, and > 1 cm for multiple nodes at the discretion of treating physician) (see section 4.4.1.5.2.1). Imaging studies prior to hormone therapy can be used to guide in the delineation of GTV-N. Alternatively for node positive patients, a CT simulation in the treatment position can be performed prior to hormone therapy to be used in fusion with CT simulation to be performed at a later date to help define the nodal volume. CTV-N will be defined as being GTV-N + 7mm margin in 3-dimensions. As always careful consideration will be made in defining CTV to carve disease out of the bowel.

Planning Target Volume

The PTV1 margins should be a minimum of 0.5 cm and a maximum of 1.5 cm in all dimensions.

4.4.1.5.2.2 Plan 2 Prostate and Proximal Seminal Vesicles Boost with IMRT

Gross Target Volume (GTV 2) See Section 4.4.1.5.2.1 above for GTV1.

Clinical Target Volume (CTV2)

The CTV2 is the GTV2 plus areas considered to contain microscopic disease, delineated by the treating physician. The CTV2 includes the GTV (prostate) plus areas at risk for microscopic disease extension plus the proximal bilateral seminal vesicles. Typically, only the proximal 1.0 cm of seminal vesicle tissue adjacent to the prostate shall be included in the clinical target volume. This 1.0 cm of seminal vesicles refers to both radial (in plane) and superior (out of plane) extent. If both prostate and seminal vesicle are visualized in the same CT slice, this seminal vesicle tissue will contribute to the 1.0 cm of tissue as seen on the CT simulation scan. For patients with clinical biopsy proven involvement of the seminal vesicles, or with imaging evidence of seminal vesicle involvement, or with clinical suspicion at the discretion of treating physician, treatment of > 1 cm of the proximal seminal vesicles (up to entire seminal vesicle), is acceptable as long as it does interfere with the ability to achieve dose constraints to the critical normal structures (see section 4.4.1.5.3).

Planning Target Volume (PTV2)

The PTV2 will provide a margin around the CTV2 to compensate for the variability of treatment set up and internal organ motion. A range of 5-10 mm around the CTV is required to define each respective PTV. Individual selection of a PTV margin should be based on the institution's level of confidence in patient set-up and the availability of image guidance. Superior and inferior margins (capping) should be 5-10 mm depending on the thickness and

spacing of the planning CT scan. Careful consideration should be made when defining the 5-10 mm margin in 3 dimensions.

4.4.1.5.3 Normal Critical Structures and Dose Constraints

Normal critical structures to be defined on the treatment planning CT scan will include the following: bladder, rectum (from its origin at the rectosigmoid flexure superiorly or the bottom of the SI joints, whichever is more inferior to the inferior-most extent of the ischial tuberosities), sigmoid colon (to the level of superior border of PTV1), bilateral femora (to the level of ischial tuberosity), penile bulb, and skin. Any small bowel within the primary beam aperture should be defined as well. The normal tissues will be contoured and considered as solid organs. The bladder should be contoured from its base to the dome, and the rectum from the anus (at the level of the ischial tuberosities) for a length of 15 cm or to the rectosigmoid flexure. This generally is below the bottom of the sacroiliac joints. If IMRT is being used to treat the pelvic nodes, the potential bowel space (not just individual loops of bowel) where the small and large bowel may

fall should be outlined. The borders are the abdominal wall anteriorly, pelvic sidewalls laterally (excluding the pelvic lymph node regions), superiorly to one cut above the last axial CT image on which the lymph nodes are outlined and inferiorly from the level of the top of PTV1 (outlining around the sides of the bladder near the top of the bladder to encompass the bowel that may fall into these regions). See the ITC web site (http://atc.wustl.edu) to view examples of target and normal tissue contours.

The following table summarizes the dose constraints for the critical structures.

	≤ 15%	≤ 20%	≤ 35%	≤ 50%		
Rectum/Sigmoid	75 Gy	70 Gy	65 Gy	40 Gy		
	10 cc < 75.6 Gy					
		20 cc < 70 Gy				
Bladder	80 Gy	75 Gy	70 Gy	50 Gy		
	90 cc < 70 Gy					
	150 cc < 65 Gy					
Potential Bowel	0.03 cc < 50.4 Gy*					
Space	50 cc < 45 Gy*					
L and R Femur	≤ 5% receives 50 Gy					
Penile bulb	Mean dose ≤ 52.5 Gy					

Table 4.4.3 Organs at Risk, and Dosimetric Constraints

While every effort should be made to deliver prescription doses to the PTV as specified while adhering to these constraints, it is recognized that certain anatomical factors may prevent this. Prescription dose reduction to a level of 77.4 Gv or 75.6 Gv is permitted if constraints cannot be met at a prescription dose of 79.2 Gy. For purposes of compliance, up to a 5% absolute increase in the volume of critical structure receiving greater than the specified dose will be considered "variation acceptable," e.g. up to 20% of the rectum may receive a dose of > 75.6 Gy without a protocol deviation. Any increase in critical structure volume greater than 5% receiving more than the specified dose will be considered a "deviation unacceptable." It is at this point that a dose reduction to 77.4 Gy or 75.6 Gy should be implemented. The prescription dose should be the maximum deliverable up to 79.2 Gy while respecting the critical normal structure constraints. Of note, the penile bulb constraint is to be regarded as a guideline, and adherence to this should not, in any way, result in a reduction of the prescription dose or compromised dose coverage of the target volume. In the event that PTV-N is in close proximity to the small bowel, absolute small bowel constraints will be prioritized over PTV-N coverage. * variation will be noted if > 50 cc to 150 cc of potential small bowel space receives \geq 45 Gy. A secondary variation will be noted if > 150 cc receives >45 Gy. However, at the discretion of the treating physician, will consider max point dose up to 55 Gy.

4.4.1.6 Treatment Verification

4.4.1.6.1 For 3DCRT: First day port films or portal images of each field along with orthogonal isocenter verification films (or images) must be obtained. If modifications are made in field shaping or design, a port film/image of each modified field along with orthogonal isocenter verification films (or images) is required on the first day's treatment of that field. Thereafter, weekly verification films or images of orthogonal isocenter views (anterior to posterior and lateral projection) are required.

For IMRT: the intensity profiles of each beam must be independently verified and compared to the planned field intensity. Portal films/images are required for IMRT but orthogonal verification films/images are required, just as for 3DCRT. Real-time ultrasound localization and on-line cone beam CT image guidance are important complements to conventional port films or portal imaging and should be used when available. Weekly port filming/imaging is required in this study.

4.4.1.6.2 Daily on-line target localization (kV or MV imaging with fiducials, kV or MV ConeBeam CT, trans-abdominal ultrasound, or other) or off-line adaptive approaches to account for interfraction organ motion and setup variability are permitted on this study. Fiducials (gold seeds) will be placed by the UT Southwestern Urology department at least 10-14 days prior to the intiation of radiation therapy date and details for this process are outlined in 4.4.2. Calypso Beacons are permitted to be used in place of gold seed fiducial markers, if monitoring intrafractional motion is desired at the discretion of the treatment team.

4.4.1.7 Quality Assurance

4.4.1.7.1 Compliance Criteria for Cases Treated with EBRT

Cases that are treated entirely with external beam radiation therapy must meet the criteria as stated in Sections 4.4.1.1 and 4.4.1.2 (see also Tables 4.4.1.1, 4.4.1.2, and 4.4.2). Both the Plan 1 and 2 requirements must be met. In addition, the critical structure dose constraints of Section 4.4.1.5.3 and Table 4.4.3 must be met.

4.4.1.7.1.1 Acceptable dose heterogeneity for external beam treatment is summarized in Tables 5.1 and 5.2. The treating physician must carefully consider the tolerance dose/volume to each critical normal structure and unspecified tissue.

4.4.1.7.2 Radiation Quality Assurance Review

The study's radiation PI or his designees will perform an RT Quality Assurance remote review after complete data for the first 4 of the cases enrolled has been made available. The study PI or his designees will perform the next remote review after complete data for the next 3 cases have been enrolled. The final cases will be reviewed within 3 months after this study has reached the target accrual or as soon as complete data for all cases enrolled has been made available, whichever occurs first. These reviews will be ongoing and performed remotely.

4.4.1.8. Radiation Therapy Adverse Events

All patients will be seen weekly by their treating radiation oncologist while undergoing EBRT. Any observations with respect to the following symptoms/side effects will be recorded: Bowel/rectal irritation manifesting as cramping, diarrhea, urgency, proctitis, or hematochezia, urinary frequency, urgency, dysuria, hematuria, urinary tract infection, or incontinence. CTCAE 4.0 will be used to grade all toxicities.

4.4.1.8.1. Clinical discretion may be used in managing radiotherapy-related side effects. Diarrhea/rectal frequency/urgency may be managed with diphenoxylate or loperamide. Bladder irritation may be mitigated with phenazopyridine. Urinary frequency/urgency can be managed with anticholinergic agents or alpha-blockers such as tamulosin. Erectile dysfunction can be managed with phosphodiesterase (PDE) inhibitors such as sildenafil.

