The maximum tolerated dose was determined to be 240 mg daily. MDV3100 demonstrated antitumor activity across endpoints in patients both with and without previous exposure to chemotherapy. The antitumor activity endpoints included prostate-specific antigen (PSA) reduction from baseline, median time to PSA progression, responses on imaging, and circulating tumor cell conversion from unfavorable to favorable counts. Three potential MDV3100-associated toxicities were identified in this study: fatigue, rash, and seizure. Three seizures (2 witnessed, 1 unwitnessed) occurred in this study at doses of 360, 480, and600 mg/day, and were reported between 26 and 48 days after initiation of MDV3100. After review of all data available from the S-3100-1-01 study, the optimal dose of MDV3100 for evaluation in Phase 3 clinical trials was determined to be 160 mg/day. A Phase 3, randomized, double-blind, placebo-controlled efficacy and safety study of oral MDV3100 (160 mg daily) in patients with progressive castration-resistant prostate cancer previously treated with docetaxel-based chemotherapy (CRPC2, also known as AFFIRM) was conducted in 1199 men, 800 of whom received treatment with MDV3100.¹¹

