4.2 Toxicities and Dosing Delays/Dose Modifications

Any subject who receives treatment on this protocol will be evaluable for toxicity. Each patient will be assessed for the development of toxicity according to the Time and Events table (Table 5.4). Toxicity will be assessed according to the NCI Common Toxicity Criteria for Adverse Events (CTCAE), version 4.0. Dose adjustments should be made according to the system showing the greatest degree of toxicity.

Enzalutamide (Xtandi, MDV3100) has been shown to be well-tolerated when used in combination with androgen deprivation (in the form of GnRH agonists or castration by orchiectomy) in completed phase I, II, and III clinical trials.

Та	ble 4.2.1 Hematological To	oxicity Dose Reductions for Enzalutamide
ANC	Platelets	Action
≥ 1,500/µL	100,000/μL	None.
1000-1499/μL	75,000-99,000/μL	 -1st Occurrence:Hold current dose until ANC ≥ 1,500/µL and platelets ≥ 100,000/µL. Do not replace missed doses. Restart next treatment at 120 mg dose. -2nd Occurrence:Hold current dose until ANC ≥ 1,500/µL and platelets ≥ 100,000/µL. Do not replace missed doses. Restart next treatment at 80 mg dose. -3rd Occurrence: Discontinue protocol therapy.
500-999/μL	50,000-74,000/μL	 -1st Occurrence:Hold current dose until ANC ≥ 1,500/µL and platelets ≥ 100,000/µL. Do not replace missed doses. Restart next treatment at 120 mg dose. -2nd Occurrence: Discontinue protocol therapy.
<500/μL	<50,000/μL	-1st Occurrence: Discontinue protocol therapy.

Table 4.2.2. Non-hematological Toxicity Dose Reductions		
NCI CTC Grade	Enzalutamide	
0-2	No change from original starting dose (with the exception of seizure)	
3-4	Hold until resolved to	
Second episode of	Hold until resolved to <grade 2,="" 80="" dose<="" mg="" reduce="" td="" then="" to=""></grade>	
grade 3 or 4 toxicity		
Third episode of	Remove subject from trial	
grade 3 or 4 toxicity		

In the randomized clinical trial of patients with docetaxel-refractory metastatic CRPC, 7 of 800 patients (0.9%) treated with enzalutamide 160 mg daily experienced a seizure. No seizures occurred in patients treated with placebo. Patients experiencing seizures were permanently discontinued from therapy and all seizures resolved. There is no clinical trial experience re-administering enzalutamide to patients who experienced seizures. Therefore, should a subject experience any seizure, enzalutamide will be discontinued and the subject removed from the trial.

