5.4 Time and Events Table

	Pre-study Days -56 to - 14	Day 1	Every 4 weeks (weeks 4- 48)	Every 8 Weeks (weeks 8-48)	Weeks 8- 10	End of study visit
Assessment						
Informed Consent	Х					
History and PE	Х	Х	Х			Х
Performance Status	Х	Х	X			Х
Toxicity Evaluations		Х	X			Х
CBC	Х	Χ*	Х			
СМР	Х	X*	Х			
PSA, testosterone	Х	Х*		X		
CXR PA/lateral or CT chest	Х					
Bone scan	X#					
CT abd and pelvis	x					
MRI pelvis	Х				Х	
TRUS-guided prostate biopsy	Х				Х	

*These tests will be repeated at day 1 if the pre-screening tests were done greater than 28 days before Day 1.

Bone scan will be performed during pre-study days – 90 to – 14.

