10.2 Sample Size and Accrual

We propose to enroll ten subjects in this pilot study. The expected accrual rate is 7 subjects over approximately 4 months. The primary endpoint is safety and tolerability of enzalutamide when combined with GnRH agonist and radiation therapy. Descriptive statistics will be computed to assess safety and tolerability. The highest AE score for each category over the 12 month period following initiation of treatment with enzalutamide plus GnRH agonist will be reported for each study subject in the summary statistics. Secondary endpoints assess mechanisms of enzalutamide plus GnRH action on prostate cancer tissue and quantitative imaging of localized prostate cancer response to enzalutamide plus GnRH therapy. As this is a pilot study, statistics will be used to report outcomes.

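### During EBRT, bowel and urinary symptoms are recorded at weekly visits that the toxicity schedule omits, so short-lived AEs outside that list can be under-captured in the primary AE summary

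*Combined protocol and SAP*

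**What the plan says.** Section 4.4.1.8 sets the visits: "All patients will be seen weekly by their treating radiation oncologist while undergoing EBRT". It then says what is to be written down at them: "Any observations with respect to the following symptoms/side effects will be recorded: Bowel/rectal irritation manifesting as cramping, diarrhea, urgency, proctitis, or hematochezia". The sentence continues with urinary frequency, urgency, dysuria, hematuria, urinary tract infection and incontinence. Fatigue, rash and skin reaction are not named. Nor is erectile dysfunction, although the next subsection covers it among radiotherapy side effects: "Erectile dysfunction can be managed with phosphodiesterase (PDE) inhibitors such as sildenafil". The same paragraph ends with a grading rule: "CTCAE 4.0 will be used to grade all toxicities".

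Section 4.2 points elsewhere for the assessment schedule: "Each patient will be assessed for the development of toxicity according to the Time and Events table (Table 5.4". In Table 5.4, toxicity evaluations fall on Day 1, under the column "Every 4 weeks (weeks 4- 48", and at the end-of-study visit. There is no weekly EBRT column. Sections 2.1.1 (monthly monitoring) and 5.2.1 (before each 28-day cycle) agree with the 4-weekly rhythm.

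These data feed the primary endpoint. Section 1.4 lists the section 4.4.1.8 toxicities as a primary endpoint measure, beside known drug toxicities and unexpected severe AEs of the combination. Section 10.2 reports, for each subject, "The highest AE score for each category over the 12 month period". Section 10.3 reports the number and nature of AEs.

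**The concern.** A count of AEs, or a worst grade over time, depends on how often someone looks. If one group of symptoms is assessed weekly and the rest every 4 weeks, the reported balance between them partly reflects the visit schedule. The difference falls in the EBRT phase, where enzalutamide, GnRH agonist and radiation are given together, a combination that section 7.7 says no completed study has examined.

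Some of the affected categories are ones the protocol itself ties to the drug. Section 1.2.2 says of the first-in-human study: "Three potential MDV3100-associated toxicities were identified in this study: fatigue, rash, and seizure". Neither fatigue nor rash is on the weekly list. Section 2.3 counts drug-related events from grade 1 upward, so mild and brief events matter to the endpoint. The sample is small: one subject is 1/7 = 14 percentage points of a category's incidence with the 7 subjects in the Study Summary, or 1/10 = 10 points with the ten in section 10.2.

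The documents also do not say how the weekly observations reach the toxicity dataset. If they enter it, ascertainment is uneven across categories. If they do not, the weekly grading of radiation toxicity, which section 1.4 relies on, adds nothing to the primary summary.

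**Working it through.** **Inputs.** EBRT lasts 8-10 weeks (section 5.2). It starts 8-10 weeks after drug start, +/- 7 days, so at weeks 7-11 (section 4.4.1). The dose is 45.0 Gy plus 34.2 Gy, at 1.8 Gy per fraction (section 4.4.1.5.1). Visits during EBRT are weekly (section 4.4.1.8). Toxicity evaluations are on Day 1 and at weeks 4, 8, ..., 48 (Table 5.4). Five fractions per week is my assumption; the documents do not state it.

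**Step 1: reproduce the EBRT duration.** 45.0/1.8 + 34.2/1.8 = 25 + 19 = 44 fractions, and 44/5 = 8.8 weeks. At the permitted 77.4 or 75.6 Gy it is 43/5 = 8.6 or 42/5 = 8.4 weeks. All lie inside the stated 8-10 weeks, so 8-10 weekly visits is a fair count.

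**Step 2: scheduled looks during EBRT.** I counted the 4-weekly visits inside the EBRT window for starts at weeks 7 to 11 in half-week steps and durations of 8, 8.8, 9 and 10 weeks. For example, a start at week 8 lasting 8 weeks contains weeks 8, 12 and 16; a start at week 9 lasting 8 weeks contains weeks 12 and 16. Of the 36 combinations, 23 contain 2 visits and 13 contain 3.

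- 4-weekly looks divided by weekly looks: from 2/10 = 0.20 to 3/8 = 0.375, mean 0.26.
- If the listed symptoms are also assessed at the 4-weekly visits: from 2/(10+2) = 0.17 to 3/(8+3) = 0.27.

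**Step 3: scheduled looks over the 12-month endpoint window.** Other categories get Day 1 plus 12 four-weekly evaluations = 13, taking the end-of-study visit as week 48. The listed symptoms get 13 + 8 = 21 to 13 + 10 = 23. The ratio is 13/21 = 0.62 to 13/23 = 0.57.

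**Step 4: from looks to events captured.** The documents give no event durations and do not say whether an evaluation takes interval history, so both are assumptions. Let an event last L days, with onset unrelated to the visit day. Let visits be T days apart, and let r be the share of events resolved before the visit that are still recalled and recorded. Then

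p = min(1, L/T), and capture = p + (1 - p) x r.

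For a 7-day event, p = 1 with weekly visits and 7/28 = 0.25 with 4-weekly visits. At 50% recall, 4-weekly capture is 0.25 + 0.75 x 0.5 = 0.625. Capture at 4-weekly visits relative to weekly visits:

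| Event duration | No recall | 50% recall | 80% recall | Full recall |
|---|---|---|---|---|
| 7 days | 0.25 | 0.625 | 0.85 | 1.00 |
| 14 days | 0.50 | 0.75 | 0.90 | 1.00 |
| 28 days or more | 1.00 | 1.00 | 1.00 | 1.00 |

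Weekly visits capture every event of 7 days or more in this model. That is complete capture, not an excess.

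**The case against.** The strongest reply is that section 4.4.1.8 does not limit recording to the list. It requires those symptoms to be recorded, does not bar others, and applies CTCAE grading to all toxicities. Section 7.3.1 defines an AE without reference to visits, and section 7.7 has AEs monitored and recorded for 12 months. A named list at a radiation visit can be read as a set of prompts. A reader might infer that nothing else may be recorded at these visits; the text does not say so. What stands is that the list has no wording such as 'including', the grading sentence names a scale rather than what is collected, and Table 5.4 leaves the visits out. The protocol does not choose between the two readings.

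Other limits also stand:

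- The one-quarter ratio counts scheduled looks during EBRT, not events captured and not the whole endpoint window.
- The list is not free of drug-type AEs. Diarrhea and hematuria are among the enzalutamide effects in section 8.1, and urinary frequency appears as pollakiuria in section 1.2.2.
- Erectile function is partly covered by the SHIM questionnaire (section 4.4.1.9), though that is given at the consult and follow-up visits and is not a CTCAE grade.
- Sections 1.4 and 10.2 together suggest that weekly radiation toxicity grades are meant to count, but no section states how they enter the dataset.
- Serious events have their own reporting route (section 7.3.5), and the stopping rules rest on AE withdrawals and SAEs. The exposure is therefore mainly in non-serious events.
- The trial is single-arm and descriptive, so no comparison between arms is biased. The AE profile is nevertheless its main product.

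**Conclusion.** The concern holds in limited form. Sections 4.4.1.8 and 4.2 with Table 5.4 set two assessment rhythms for the EBRT phase and do not reconcile them. Read as written, bowel and urinary symptoms get about 8-10 scheduled looks and other categories 2-3, a ratio of 0.20-0.375. Over 12 months the ratio is 0.57-0.62. Short-lived, non-serious AEs outside the list can be under-captured relative to those on it. Relative capture runs from 1.00 (events of 28 days or more, or full recall) to 0.25 (7-day events, no recall). Where the trial would fall in that range cannot be determined from the documents.

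Three stronger conclusions are tempting and not supported. The combined phase will not show more pelvic toxicity than occurred, because extra looks find events and do not create them. A distorted primary profile is possible but not demonstrated, since it depends on durations and recall that the documents do not give. Nothing in the documents ranks fatigue and skin reaction as the most important overlap between drug and radiation; section 7.7 names seizure as the most prominent safety concern.

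**What to change.** Make three linked changes:

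1. Add a weekly EBRT column to Table 5.4 with a toxicity evaluation.
2. In section 4.4.1.8, state that all AEs are collected and graded by CTCAE 4.0 at the weekly visits, and keep the bowel and urinary list as prompts.
3. In section 10.2, state that weekly grades enter the highest-grade summary for every category.

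Scheduled looks for the other categories during EBRT would rise from 2-3 to 10-13 (8 + 2 to 10 + 3), and over 12 months from 13 to 21-23, equal to the bowel and urinary symptoms.

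The visits already take place, so the cost is a few more CRF entries. Reported rates of other AEs may be slightly higher.
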